4.5.5 C-SSRS Data

The Columbia Suicide Severity Rating Scale (C-SSRS) is an assessment that evaluates suicidal ideation and behavior. There are 5 "Yes/No" questions on suicidal ideation following the increasing severity order: (1) Wish to be dead, (2) Non-specific active suicidal thoughts, (3) Active suicidal ideation with any methods (not plan) without intent to act, (4) Active suicidal ideation with some intent to act, without specific plan, (5) Active suicidal ideation with specific plan and intent, and 6 "Yes/No" questions on suicidal behavior following the increasing severity order: (6) Preparatory acts or behavior, (7) Aborted attempt, (8) Interrupted attempt, (9) Actual attempt, (10) Suicidal behavior, (11) Suicide (only at post-baseline visits). Another "Yes/No" question of whether the subject has engaged in non-suicidal self-injurious behavior is also collected.

In the summary table for C-SSRS, number of subjects who answered "Yes" to each of the 11 questions post-baseline, subjects who answered "Yes" to at least one question for suicidal ideation, subjects who answered "Yes" to at least one question for suicidal behavior, and subjects who have engaged in non-suicidal self-injurious behavior will be presented. A listing of subjects with any suicidal ideation or behavior at baseline or post-baseline will be provided.

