4.5 Safety Analysis

4.5.1 General Considerations

Analysis population

Safety population will be used for safety analyses of AEs, clinical laboratory data, Columbia Suicide Severity Rating Scale (C-SSRS) data, ECG data and vital sign data (all the safety data except for ARIA data). Safety MRI population will be used for analyses of ARIA data.

Final V1.0

Safety treatment groups

Different from the randomization treatment groups, if a subject who was randomized to placebo group accidentally received one or more doses of the active treatment during the study, he/she will be classified as either low or high dose group for all the safety analyses, depending on the ApoE status and the maximal dose level of the active treatment received (Table 5). A listing of such subjects will be provided, as described in section 4.2.5. Safety treatment groups will be the same as the randomization treatment groups for other subjects (subjects randomized to active treatment groups, and subjects randomized to placebo without any accidental active dose). Safety treatment groups will be used for all the safety analyses unless otherwise specified.

Table 5: Safety treatment groups for placebo subjects with accidental active treatment

Randomization treatment group	Randomization ApoE status	Safety treatment group classification based on the maximum dose level of the accidental active treatment		
		>0 to 3 mg/kg	>3 to 6 mg/kg	>6 mg/kg
Placebo	ΑροΕ ε4 (+)	Low dose	High dose	High dose
	ΑροΕ ε4 (-)	Low dose	Low dose	High dose

Safety analysis displays

AEs, clinical laboratory data, C-SSRS data, ECG data and vital sign data (all the safety data except for ARIA data) will be summarized by treatment group (placebo, low dose, high dose and BIIB037 total; analysis display A in Appendix 6.1), unless otherwise specified. All the ARIA related tables will be presented by treatment group stratified by ApoE status (3 columns under each treatment group: ApoE ϵ 4+, ApoE ϵ 4- and total; analysis display B in Appendix 6.1), unless otherwise specified. A subset of AE tables will also be presented by treatment group stratified by ApoE status in addition to by treatment group. All the listings will be presented by treatment group stratified by ApoE status.

Incidence, incidence proportion and incidence rate

Incidence and incidence proportion will be provided in incidence tables. Incidence is
defined as the number of subjects who experienced an event. Incidence proportion is

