4.5.2 Clinical Adverse Events

Treatment-emergent AEs (TEAEs)

All AEs will be analyzed based on the principle of treatment emergence. A treatment-emergent AE was defined as an AE that started or worsened after the start of first infusion of study treatment.

To define treatment emergence for AEs with missing start or stop date or time the following additional criteria will be used:

- if both the start and stop dates for a particular AE are missing, then that AE is considered treatment emergent;
- if the start date for a particular AE is missing and the stop date/time falls after the first dose date/time, then that AE is considered treatment emergent;
- if the start date for a particular AE was the same as the first dose date, and the start time was missing, then that event is considered treatment emergent.

For AEs with a partial start date, the year/month of the event date will be compared to that of the first dosing date to determine whether the event is treatment emergent.

In addition, SAEs that occurred since a subject was screened in the study and prior to the first infusion of study treatment, which by definition are not treatment-emergent, will be analyzed separately.

Only TEAEs will be included in the AE tables, unless otherwise specified. Listings of AEs will include all events, whether treatment-emergent or not.

As specified in the protocol, subjects were expected to return to the study site for an End of Study visit 18 weeks after the last administration of study treatment. However, some subjects may elect to continue study participation on a modified schedule after discontinuing treatment, possibly in substantial excess of 18 weeks. For most general AE summaries, AEs

Final V1.0

with an onset more than 18 weeks after the last dose will be excluded (will specify in the footnote of the specific table). For incidence rate analyses excluding AEs more than 18 weeks after the last dose, the "last day on study" in follow-up time calculation will be replaced with "18 weeks after last dose or last day on study, whichever earlier". Summaries of deaths and AEs leading to study withdrawal, and other selected analyses will include all AEs regardless of the time since the last dose. Listings will include all AEs, unless otherwise specified.

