4.5.4.2 Qualitative analyses

For all qualitative analyses, all values will be included (not just the "analyzed record" within each visit window in the quantitative analyses).

Shift analyses

Laboratory data will be summarized using shift tables where appropriate. Each subject's hematology, blood chemistry and urinalysis numeric values will be flagged as "low", "normal", or "high" relative to the normal ranges of the central laboratory or as "unknown" if no result is available. Each subject's urinalysis categorical values will be flagged as "positive" or "negative", or "unknown" if no value is available.

Shifts from baseline to high/low status will be presented for hematology, blood chemistry and urinalysis numeric parameters, and shifts from baseline to abnormal (positive) will be presented for urinalysis categorical parameters. Shift to low includes normal to low, high to low, and unknown to low; Shift to high includes normal to high, low to high, and unknown to high. Subjects need to have at least one post-baseline evaluation and a baseline value not low or high or positive (including missing) in order to be included in the analysis. A listing of laboratory normal ranges will be provided.

Grade analyses

Worst post-baseline grade will be summarized for each laboratory parameter in both exclusive way and cumulative way. Subjects need to have at least one post-baseline evaluation in order to be included in the analysis. Common Toxicity Criteria for Adverse Events v4.0.3 (CTCAE) published on 2010-06-14 will be used for grade determination. Grade determination is based solely on laboratory values not taking AEs into account.

Potentially Clinically Significant laboratory abnormalities analyses

For hematology, blood chemistry and urinalysis, the number of subjects with potentially clinically significant laboratory abnormalities post-baseline will be summarized for the parameters provided in Table 8. Subjects need to have at least one post-baseline evaluation and a baseline value not potentially clinically significant (including missing) in order to be included in the analysis.

Table 8: Criteria to Determine Potentially Clinically Significant (PCS) Laboratory Abnormalities

Clinical Laboratory Outlier Criteria			
Parameter name	PCS Low	PCS High	
HEMATOLOGY			

Final V1.0

Clinical Laboratory Outlier Criteria				
Parameter name	PCS Low	PCS High		
White blood cells	<3.0 x 10 ⁹ /L	$>16 \times 10^9/L$		
Lymphocytes	<0.8 x 10 ⁹ /L	>12 x 10 ⁹ /L		

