3.5.5 C-SSRS Data

The Columbia Suicide Severity Rating Scale (C-SSRS) is an assessment that evaluates suicidal ideation and behavior. There are 5 "Yes/No" questions on suicidal ideation following the increasing severity order: (1) Wish to be dead, (2) Non-specific active suicidal thoughts, (3) Active suicidal ideation with any methods (not plan) without intent to act, (4) Active suicidal ideation with some intent to act, without specific plan, (5) Active suicidal ideation with specific plan and intent, and 6 "Yes/No" questions on suicidal behavior following the increasing severity order: (6) Preparatory acts or behavior, (7) Aborted attempt, (8) Interrupted attempt, (9) Actual attempt, (10) Suicidal behavior, (11) Suicide (only at post-baseline visits). Another "Yes/No" question of whether the subject has engaged in non-suicidal self-injurious behavior is also collected.

The summary table for C-SSRS will be conducted for the placebo-controlled and LTE active treatment period. Number of subjects who answered "Yes" to each of the 11 questions post-baseline, subjects who answered "Yes" to at least one question for suicidal ideation, subjects who answered "Yes" to at least one question for suicidal behavior, and subjects who have engaged in non-suicidal self-injurious behavior will be presented. A listing of subjects with any suicidal ideation or behavior at baseline or post-baseline will be provided for placebo-controlled and LTE period.

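### The C-SSRS tables do not use the baseline answer, so recurring suicidal ideation or behaviour is tabulated together with new cases

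*SAP*

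**What the plan says.** Placebo-controlled SAP, Section 4.5.5, describes five ideation questions and six behaviour questions, each set in increasing order of severity, plus a question on non-suicidal self-injury. The table counts subjects with a Yes "to each of the 11 questions post-baseline", then "subjects who answered 'Yes' to at least one question for suicidal ideation", a matching row for behaviour, and a self-injury row. The words restricting the count to post-baseline answers stand only with the 11 questions.

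The baseline answer appears in one output: "A listing of subjects with any suicidal ideation or behavior at baseline or post-baseline will be provided". It clearly is collected, because the section marks completed suicide as the one item asked only after baseline.

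The denominator is not restricted by baseline status. Section 4.5.1 states: "Safety population will be used for safety analyses of AEs, clinical laboratory data, Columbia Suicide Severity Rating Scale (C-SSRS) data".

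The LTE SAP, Section 3.5.5, uses the same rows and says: "The summary table for C-SSRS will be conducted for the placebo-controlled and LTE active treatment period". Section 3.1.2 of that SAP limits late-start subjects to LTE data in this period, and the general considerations in its Section 3.5 set the LTE baseline for them.

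**The concern.** A safety table of this kind is normally read for what emerged on treatment. Here a recurring case and a new case land in the same cell.

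Several other domains in the same SAP do provide a summary that uses baseline, so the C-SSRS section stands out in having none. In the placebo-controlled period the cost is a diluted contrast between arms. In the LTE active-treatment period every subject is on aducanumab, so no concurrent control column shows how many Yes answers would have recurred anyway.

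**Working it through.** The SAP states no C-SSRS rate, sample size or power, so there is no planned figure to reproduce. The check is a comparison of rules, followed by an illustration of size.

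**Rules side by side (placebo-controlled SAP)**

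| Domain | Use of baseline |
|---|---|
| AEs, 4.5.2 | "All AEs will be analyzed based on the principle of treatment emergence" |
| Laboratory shifts, 4.5.4.2 | Restricted by baseline status; a missing baseline is allowed |
| Potentially clinically significant laboratory values, 4.5.4.2 | Requires "a baseline value not potentially clinically significant (including missing) in order to be included in the analysis" |
| ECG, 4.5.6 | Shift from a normal or unknown baseline |
| Antibodies, 4.7.1 | Negative at baseline, or more than a 2-fold rise in titre |
| Worst CTCAE grade, 4.5.4.2 | None |
| Hepatotoxicity, 4.5.4.2 | None |
| Absolute vital-sign limits, 4.5.7 | None |
| C-SSRS, 4.5.5 | None in any table; listing only |

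The SAP uses both approaches. Laboratory and vital-sign data have unconditioned summaries alongside others that use baseline: shifts and potentially clinically significant values for laboratory data, change from baseline for vital signs. C-SSRS has only the unconditioned kind.

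**Illustration for one active arm against placebo**

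Inputs:
- n = 535 per arm (SAP Section 3).
- p0, p1: new-onset proportions on placebo and active. These are assumptions.
- c: share of subjects with a baseline Yes who answer Yes again after baseline, taken as equal in the two arms. This is an assumption.

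Formulas:
- Planned count as a proportion: c + (1 − c)·p.
- New-onset count: p, among the n·(1 − c) remaining subjects.
- Power, two-sided 0.05: Φ((d − 1.96·SE0)/SE1), where d is the difference, SE0 the pooled and SE1 the unpooled standard error.

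Worked case, p0 = 3%, p1 = 6%, c = 5%:
- Placebo: 0.05 + 0.95 × 0.03 = 7.85%.
- Active: 0.05 + 0.95 × 0.06 = 10.70%.
- Risk ratio: 10.70/7.85 = 1.36. Risk difference: 2.85 points.

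| p0, p1 | c | Placebo / active as tabulated | Risk ratio | Risk difference (points) | Power, planned count | Power, new onset only |
|---|---|---|---|---|---|---|
| 3%, 6% | 0 | 3.00% / 6.00% | 2.00 | 3.00 | 66% | 66% |
| 3%, 6% | 1% | 3.97% / 6.94% | 1.75 | 2.97 | 57% | 65% |
| 3%, 6% | 3% | 5.91% / 8.82% | 1.49 | 2.91 | 45% | 65% |
| 3%, 6% | 5% | 7.85% / 10.70% | 1.36 | 2.85 | 36% | 64% |
| 1%, 3% | 0 | 1.00% / 3.00% | 3.00 | 2.00 | 65% | 65% |
| 1%, 3% | 1% | 1.99% / 3.97% | 1.99 | 1.98 | 48% | 64% |
| 1%, 3% | 5% | 5.95% / 7.85% | 1.32 | 1.90 | 23% | 63% |

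The new-onset count keeps the risk ratio at 2.00 or 3.00 throughout. The power columns only express loss of signal, because no C-SSRS test is planned.

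**The case against.** The strongest case on the other side has five parts.

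- **The count is complete and honest.** Every Yes in the 11 question rows is a real post-baseline answer, and no on-treatment case is dropped. This stands, and it is why those rows should stay.
- **No general rule is broken.** Treatment emergence is stated for AEs, and the CTCAE grades, hepatotoxicity criteria and absolute vital-sign limits are also unconditioned. This stands: the gap is a missing summary, not a contradiction.
- **The information is not lost.** The listing shows baseline and later status, the question rows are ordered by severity, and ideation reported as an AE falls under treatment emergence. This stands in part. Separating cases by hand in a three-arm study of about 1605 subjects is a poor substitute for a row in a table.
- **The size is unanchored.** The new-onset rates and c are all assumed, the risk difference hardly moves, and the effect vanishes at c = 0. Entry criteria in the protocol, which is not at hand, may keep c small. This stands.
- **The LTE rules already help.** Late-start subjects contribute only LTE data to the active-treatment period, and the LTE baseline is already set for them. This stands, but no C-SSRS row makes use of that baseline.

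A reader might infer that any ideation present before dosing is counted as an on-treatment event. The text does not support that for the 11 question rows: ideation reported only before dosing does not enter them, and a further Yes after baseline is needed. For the same reason, ideation confined to the placebo period does not enter those rows for late-start subjects in the LTE table.

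**Conclusion.** The point holds as a minor one. Neither C-SSRS table separates recurring from new or worsened ideation or behaviour, although the data to do so are collected.

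In the placebo-controlled period the consequence is attenuation of the risk ratio towards 1, with little change in the risk difference and no expected advantage to any arm, since randomisation balances the recurring cases. Its size depends on a recurring-case share that the SAP does not give. The illustrated fall from 2.0 to between 1.75 and 1.36 rests wholly on assumed rates.

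The gap matters more in the LTE active-treatment table, where there is no concurrent placebo and the table alone cannot show whether a Yes is new. A reader might go further and infer a bias or a masked safety signal. The documents support neither.

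**What to change.** In Section 4.5.5 and in LTE SAP Section 3.5.5, keep the existing rows and add:

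1. Subjects with a post-baseline Yes for ideation and none at baseline, and the same for behaviour.
2. Subjects whose worst post-baseline ideation category is higher than at baseline, using the severity order already given in both sections.

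State in LTE Section 3.5.5 that these rows use the placebo-controlled baseline for early-start subjects and, for late-start subjects, the LTE baseline already set in that SAP's general safety considerations.

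Add the post-baseline qualifier to the any-ideation, any-behaviour and self-injury rows in both sections, so that a programmer cannot include baseline answers in them.

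The cost is a few extra rows in two tables. No new data are needed, and efficacy and blinding are unaffected.

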4.5.6 ECG Data

Shift from normal or unknown ECG at baseline to abnormal, not adverse event or abnormal, adverse event post-baseline ECG will be summarized for the placebo-controlled period. Subjects with abnormal post-baseline ECG status will be listed.

4.5.7 Vital Sign Data

Vital sign parameters include body temperature, systolic blood pressure, diastolic blood pressure, heart rate, respiration rate and weight. Vital signs will be measured with the subject supine and after the subject has been resting for at least 10 minutes. The descriptive statistics for actual values and change from baseline will be summarized at each visit. Plot of mean vital sign values at each visit will be provided.

The analysis of vital signs will also focus on the incidence of clinically relevant outliers based on the following criteria. The incidence and percentage of clinically relevant outliers determined by each criterion will be summarized. A listing of subjects with clinically relevant vital signs will be provided.

Table 9: Criteria Used to Assess Potential Clinically Relevant Outliers in Vital Signs

Variable	Low	High
Systolic Blood Pressure	<90 mm Hg or ≥20 mm Hg	>180 mm Hg or ≥20 mm Hg
	decrease from Baseline (BL)	increase from BL

Final V1.0

Diastolic Blood Pressure	< 50 mm Hg or ≥15 mm Hg decrease from BL	>105 mg Hg or ≥15 mm Hg increase from BL
Heart Rate	$<$ 50 bpm or \ge 15 bpm decrease from	$>$ 120 bpm or \geq 15 bpm increase
	BL	from BL
Temperature	>2 degree C decrease from BL	>38.5 C or >2 degrees C increase
		from BL
Respiration Rate	< 10 breaths per minute or $\ge 50\%$	>25 breaths per minute or \(\geq 50\%\)
	decrease from BL	increase from BL
Weight	≥7% decrease from BL	≥7 % increase from BL
BL= baseline; bpm = beats po	er minute	

Visit windows for by visit summaries

For vital sign by visit summaries, the analysis visit should be defined using windows (see Table 10 below). If there is more than 1 value in the same analysis visit window for a certain parameter for a subject, then the closest record to the target visit day will be used for the by visit analysis. If there are 2 values in the same analysis visit window with the same distance from the target visit day for a certain parameter for a subject, then the record with the later date will be used for the by visit analysis.

Table 10: Visit Windows for Vital Sign by Visit Summaries

Analysis visit	Target visit day	Analysis visit window
Baseline	1	Most recent non-missing pre-dose value
Week 4	29	[2, 42]
Week 8	57	[43, 70]
Week 12	85	[71, 98]
Week 16	113	[99, 126]
Week 20	141	[127, 154]
Week 24	169	[155, 182]
Week 28	197	[183, 210]
Week 32	225	[211, 238]
Week 36	253	[239, 266]
Week 40	281	[267, 294]
Week 44	309	[295, 322]
Week 48	337	[323, 350]
Week 52	365	[351, 378]
Week 56	393	[379, 406]
Week 60	421	[407, 434]
Week 64	449	[435, 462]
Week 68	477	[463, 490]
Week 72	505	[491, 518]
Week 76	533	[519, the end day of the placebo-controlled period*]

^{*} The end day of the placebo-controlled period is the last day before the first infusion in LTE for subjects who enter LTE, and is the last day in study for subjects who do not enter LTE.

4.6 Pharmacokinetics Analysis

The PK analysis population will be used for the description of the concentration-time profiles and for the estimation of PK parameters. Randomization treatment groups will be used for

Final V1.0

PK analysis. Tables and figures, if not otherwise specified, will be presented by treatment group stratified by ApoE status (3 columns under each treatment group: ApoE ϵ 4+, ApoE ϵ 4- and total; analysis display B in Appendix 6.1). Listings will be presented by treatment group stratified by ApoE status.

PK evaluation will be based on the concentration of aducanumab in serum samples collected prior to infusion and between 10 and 60 minutes after completion of the infusion and line flush for the visits specified per protocol.

Concentrations of aducanumab that are below the limit of quantification (BLQ) will be imputed as 0. When summarizing concentrations or PK parameters in serum, a minimum of 2 values are required to show the arithmetic mean and geometric mean, and at least 3 values are required to show the standard deviation and coefficient of variation.

4.6.1 Serum Concentration Profile

Serum concentration data will be summarized by nominal visit. Number of evaluable subjects, arithmetic mean, standard deviation, median, 25% and 75% quartiles, minimum, maximum, geometric mean, and coefficient of variation will be presented at each visit. A listing of individual concentration data will be provided.

A semi-logarithmic plot of the mean serum concentration-time curves of aducanumab from first visit to last visit through nominal times will be provided.

4.6.2 Serum PK Parameters

Two PK parameters C_{max} and C_{min} will be computed by noncompartmental methods, as data permit, from serum concentration-time data:

Parameter	Definition	Units
C _{max}	Observed maximum serum aducanumab concentration	ug/mL
Cmin	Observed minimum serum aducanumab concentration	ug/mL

Number of evaluable subjects, arithmetic mean, standard deviation, median, 25% and 75% quartiles, minimum, maximum, geometric mean, and coefficient of variation will be presented for the PK parameters.

4.6.3 Subgroup analysis for protocol version 4

Due to the change in maximal dose from 6 mg/kg to 10 mg/kg for ApoE &4 carrier high dose group in protocol version 4, not all subjects have had opportunity to receive the protocol specified high dose (6 doses in titration before receive 10mg/kg) in the placebo-controlled period. Summary tables for serum concentration and PK parameters will be provided for ApoE &4 carriers who were randomized to the high dose group, stratified by the expected number of doses at 10 mg/kg (categories of 0, 1-6, 7-13, 14, and a total column of having at least one dose) a subject would have received based on the first infusion date and the date consenting to protocol version 4.

Final V1.0

